Since the device implant will occur outside of the study and the study requires participants to be stable on cDBS prior to enrollment, the standard deviation of the change from cDBS to aDBS in “On” time

without troublesome dyskinesia will be used to establish a threshold for assessing the performance goal. The threshold will be set as 1 standard deviation. If the difference between aDBS and cDBS (aDBS-cDBS) for a subject is at least -1 standard deviation, the threshold will be met for the subject. Using this threshold, the proportion of subjects who exceed the threshold will be computed.

The sample size was estimated using a binomial distribution for a one-sided exact test (alpha=0.0125) for a proportion (PASS 2011 module Tests for One Proportion [Differences]) to compare to a performance goal of 50%. Assuming the alternative hypothesis of 85% of subjects exceeding the threshold, a minimum of 36 subjects achieves at least 90% power to reject a performance goal of 50%.

Simulations have shown that this sample size is sufficient to cover possible deviations from normality such as a uniform distribution. The threshold criterion will remain the same as the standard deviation is robust to moderate departures from normality.

Sample size in the Primary Cohort may be increased to a maximum of 55 subjects for whom at least 1 aDBS mode is acceptable and who enter the aDBS Evaluation Phase to obtain at least 8 subjects per aDBS mode and 8 subjects per target site (Subthalamic Nucleus [STN]/ Globus Pallidus [GPi]). Criteria for increasing sample size is described in section 7.2.1.

For the safety analyses, a minimum of 30 subjects followed for approximately 30 days with aDBS out-of-clinic in the subjects' real-world environments provides at least 95% probability that all events with a true event rate of at least 10% would be reported at least once.

It is estimated that approximately 70-100 subjects implanted with a commercially available Medtronic DBS system with Percept PC INS will be enrolled in the study to obtain 40 subjects for whom at least 1 aDBS mode is acceptable and who enter the aDBS Evaluation Phase. Accounting for a 10% dropout during the aDBS Evaluation Phase, a minimum of 36 subjects (at least 8 per brain target site (STN/GPi) and 8 per aDBS mode) will complete the aDBS Evaluation phase.

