7.9.1.4 Analysis methods

The primary analysis will use the FAS as described in section 7.1.3. The PD Home Diary will be collected for at least 3 consecutive days (24 hour “periods”) prior to each visit to evaluate the primary objective. Complete diary periods collected anytime during the cDBS Baseline period will be used for analysis as subjects should be on stable cDBS stimulation from enrollment through the end of this period. In the aDBS Evaluation Phase, diary periods will be defined starting with the first completed diary record which is no more than 14 days prior to the visit. If diary is collected more than 14 days prior to the visit, the diary may be used for analysis if there is no change in aDBS stimulation settings. Complete diary periods are defined as any diary period where at least 21 hours (defined as 42 30-minute records) of diary were completed during the 24-hour period, and only complete periods will be used for analysis. If the diary is collected for more than 3 complete periods, up to 7 which are closest to the visit will be used for the analysis, while if a subject has zero complete periods, their diary will be considered missing. Diaries with at least 1 complete period available will be used for analysis. Data from non-contiguous complete periods may be used in the analysis.

The change in daily “On” time without troublesome dyskinesia from cDBS to aDBS will be computed for each subject. The overall standard deviation of the change will be computed for the FAS. The threshold will be set as 1 standard deviation. If the difference between aDBS and cDBS (aDBS-cDBS) for each subject is at least -1 standard deviation, the threshold will be met for the subject. Using this threshold, the proportion of subjects who exceed the threshold will be computed. The proportion with “On” time without troublesome dyskinesia during the respective aDBS Evaluation Period that exceed the threshold will be compared to the performance goal of 50% for each aDBS mode separately using a binomial exact test. The objective will be considered passed if the p-value is less than 0.0125. The lower bound of the 97.5% confidence interval will also be presented.

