7.9.1.5 Handling of missing data

All attempts will be made to minimize missing data. If 5% of the data or fewer are missing (as defined in section 7.9.1.4) for the analysis, no imputation will be used and the data will be analyzed as specified in the previous section. Otherwise, if missing data are observed, multiple imputation will be used for the analysis of the key primary objective.

Prior to the MI, the distribution of the continuous variables will be assessed for normality (using the Shapiro-Wilk test) to determine whether regression ($P \geq 0.05$) or predictive mean matching ($P < 0.05$) multiple imputation will be used for each variable. First, multiple imputation will be applied to impute missing values in continuous hours of “On” time without troublesome dyskinesia for each mode separately (aDBS single threshold, aDBS dual threshold). The model variables in the MI analysis may include, as appropriate:

- target site (STN or GPi)
- cDBS hours of “On” time without troublesome dyskinesia
- Age
- Gender
- Center
- PD duration

Variables will be ordered in the model based on the level of missingness (from least to most missing) and in the order specified above when the missingness is equal for 2 or more variables.

The fully conditional specification (FCS) method within SAS (version 9.4 or higher) with 5 repetitions and 100 burn-in iterations will be used for imputation. No limits will be defined for imputed values.

Following imputation, the “On” time without troublesome dyskinesia will be assessed against the “On” time threshold, and the estimate for the proportion of subjects meeting threshold will be determined for each imputation and combined using MI analysis methods. The lower bound of the 97.5% confidence limit will be determined using the MI Clopper-Pearson mean success approach⁵. In addition, the objective will be tested by comparing the lower bound of the 97.5% confidence limit to 50% for each imputation, and the overall p-value will be computed as the median of the p-values from the multiply imputed datasets.⁶

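### With only 5 imputations behind the median p-value, a borderline primary result can pass or fail depending on the random draw, and the 97.5% bound tested beside it has no stated tail

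*SAP*

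**What the plan says.** **Pass criterion.** SAP 7.9.1.4 (and CIP 13.4.4) applies an exact binomial test to each mode: "The objective will be considered passed if the p-value is less than 0.0125". A lower 97.5% bound is reported in addition.

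**Missing data.** SAP 7.9.1.5 uses no imputation if 5% or less of the data are missing. Above that, missing hours are imputed separately for each mode, "with 5 repetitions and 100 burn-in iterations will be used for imputation". Each imputed dataset is tested by comparing the lower 97.5% bound with 50%, and "the overall p-value will be computed as the median of the p-values from the multiply imputed datasets". A pooled lower bound, built on mean successes, is also calculated. CIP 13.4.5 describes the same scheme.

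**Planned size.** SAP section 6 aims "to obtain 40 subjects for whom at least 1 aDBS mode is acceptable" and allows for 10% dropout, leaving at least 36 completers. On power it says: "Assuming the alternative hypothesis of 85% of subjects exceeding the threshold, a minimum of 36 subjects achieves at least 90% power".

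**The concern.** Each imputed dataset yields a whole number of successes, and the exact test passes or fails at one count. When the observed count lies close to that limit, each imputed dataset is in effect a random vote. The median p of 5 datasets is below 0.0125 exactly when at least 3 of the 5 votes pass. A majority of five is an unstable summary, so the same trial data can pass with one seed and fail with another.

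The second issue is the 97.5% bound. The test level is 0.0125 one-sided. A two-sided 97.5% interval has a lower tail of 0.0125 and matches it. A one-sided 97.5% bound has a tail of 0.025 and does not. The section tests this bound against 50% without saying which is meant.

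At stake is the primary verdict for a mode in a pivotal trial. If the result is close, the sponsor would have to defend a verdict that another random draw might reverse.

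**Working it through.** **Inputs.** One-sided exact test, alpha 0.0125, null 50%, planned rate 85%, 36 completers, 40 entering (SAP section 6); p < 0.0125 to pass (SAP 7.9.1.4); imputation above 5% missing, 5 imputations, median p (SAP 7.9.1.5).

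**The plan's own figure.** For n = 36 the exact test needs 26 successes (actual alpha 0.0057), and power at 85% is 98.6%. This agrees with the stated floor of 90%. Also 36 / 0.9 = 40.

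**Is imputation triggered?** Assume that all 40 subjects are eligible for both modes and that 4 drop out with no usable diary for the periods lost.
- All 4 in period 1: both modes lost, 4/40 = 10% per mode. Triggered.
- 2 in period 1 and 2 in period 2 (one per mode): (2 + 1)/40 = 7.5%. Triggered.
- All 4 in period 2, split evenly: 2/40 = 5%. Not triggered.

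**Count needed at N = 40.** 28 successes give p = 0.0083 and 27 give p = 0.0192, so 28 are needed.

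**Seed dependence, 36 observed and 4 missing.** Let S be the observed successes, and assume that each missing subject is imputed as a success with probability S/36.
- One imputed dataset passes with probability q = P(Bin(4, S/36) ≥ 28 − S).
- The median of m p-values passes with probability P = P(Bin(m, q) ≥ (m + 1)/2).
- Two independent seeds disagree with probability 2P(1 − P).

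For S = 25: q = 4 × (25/36)³ × (11/36) + (25/36)⁴ = 0.642. With m = 5, P = 0.752, and 2 × 0.752 × 0.248 = 0.373.

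| S of 36 | q | P, m = 5 | Disagree, m = 5 | Disagree, m = 25 | Disagree, m = 101 |
|---|---|---|---|---|---|
| 24 | 0.198 | 0.056 | 11% | 0.1% | about 0% |
| 25 | 0.642 | 0.752 | 37% | 13% | 0.4% |
| 26 | 0.932 | 0.997 | 0.6% | about 0% | about 0% |
| 27 | 0.996 | 1.000 | about 0% | about 0% | about 0% |

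**Averaged over trials** (weighting by the binomial distribution of S):

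| True success rate | m = 5 | m = 101 |
|---|---|---|
| 85% (planned) | 0.4% | below 0.01% |
| 75% | 4.9% | 0.04% |
| 70% | 6.7% | 0.05% |

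With 3 missing (37 observed, the 7.5% case), the m = 5 averages are 0.3%, 3.9% and 5.6%.

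**Check with continuous data.** A simulation used normal changes, regression imputation on cDBS hours, the SD threshold recomputed in each imputed dataset, m = 5, 1,500 datasets and 20 seeds each. Two seeds disagreed in 0.45% of cases with no mean change (about 84% of a normal distribution lies above −1 SD). They disagreed in 8.7% when the mean change was −0.48 SD; there 28% of datasets did not give the same verdict with all 20 seeds.

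**Bound against test.** Clopper-Pearson lower bounds at N = 40:

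| Successes | p | Bound, tail 0.0125 | Bound, tail 0.025 |
|---|---|---|---|
| 27 | 0.0192 (fail) | 48.6% (fail) | 50.9% (pass) |
| 28 | 0.0083 (pass) | 51.2% (pass) | 53.5% (pass) |

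With a tail of 0.0125 the bound and the test agree in a single dataset. With 0.025 they conflict at 27 of 40, and no randomness is involved.

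**The case against.** The strongest reply is that this hardly matters if the trial goes as planned. At a true rate of 85%, counts of 24 or 25 out of 36 arise in about 1.2% of trials, and seeds disagree in about 0.4%. The larger figures require aDBS to do clearly worse than assumed. The complete-case analysis needs no imputation and would be reported as well. All of this stands and limits the size of the point. It does not remove it, because the complete-case result is only a sensitivity analysis and a pass rule is needed most when the result is close.

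A reader might infer more from these passages than they support:
- *That two rival pass rules exist.* SAP 7.9.1.4 makes p < 0.0125 the criterion and presents the bound alongside it. The fault is narrower: 7.9.1.5 describes a bound comparison as a test and leaves its tail unstated.
- *That imputation is bound to happen.* The dropout arithmetic shows that it may not for a given mode. One complete 24-hour diary period also keeps a diary from counting as missing.
- *That no seed is specified.* The SAP's revision history mentions example imputation code, and code is blacked out in the public copy. A seed may be there.
- *That the pooled bound should replace the median p because it carries between-imputation variance.* If it is Clopper-Pearson at the mean count, it carries none. The cited source is not available to settle this.
- *That the imputation model is wrong because it lists center and omits the subject's other-mode value.* The list is optional: "The model variables in the MI analysis may include, as appropriate". The benefit of the other-mode value was not tested, and single-mode subjects have none.
- *That TEED has the same problem.* SAP 7.9.2.6 also uses 5 imputations, but pools a mean with a t-statistic. There is no median p and no discrete count, and no TEED calculation was made here.

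**Conclusion.** The point holds as a robustness gap confined to borderline results. With N = 40, 4 missing and 5 imputations, the primary verdict for a mode depends materially on the seed at 24 or 25 observed successes out of 36 (11% and 37% disagreement). Over all trials the risk is about 0.4% at the planned 85%, 4.9% at 75% and 6.7% at 70%. Separately, the untailed 97.5% bound can contradict the test at 27 of 40 if it is read as one-sided.

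The seed figures assume that missing subjects are imputed at the observed success rate; the continuous simulation gives the same order of size. They also take 40 subjects per mode, the most the planned enrolment allows, since some subjects may have only one acceptable mode. The documents do not support a claim that the planned analysis is likely to give the wrong answer in the expected scenario.

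**What to change.** In SAP 7.9.1.5 and CIP 13.4.5:

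1. Raise the number of imputations from 5 to at least 100. An odd number such as 101 makes the median a single p-value. Pre-specify the seed if the blacked-out code does not already do so.
2. State that p < 0.0125, with p the median over imputations, is the single pass criterion and that the confidence bound is supportive.
3. Define the bound with a lower tail of 0.0125 (two-sided 97.5%), so that it matches the test.

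The median-p rule and the predictor list can stay. More imputations help less if a single imputed dataset is close to a coin flip: with 38 observed, 2 missing and 26 successes, disagreement falls only from 49% to 39% at 101. At N = 40 that pattern is exactly 5% missing and would not be imputed, but it shows why the seed should be fixed as well. The cost is seconds of computing time and a wording change in both documents.

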7.9.1.6 Supporting analyses

Supporting analyses for the primary objective in the Primary Cohort include verifying the lack of a period or carryover effect (randomized subjects only), a target site effect (STN/GPi), a lead type effect (legacy Models 3387 and 3389 compared to SenSight Models B33005 and B33015), or a center effect.

Summarized results from the Directional Stimulation Cohort will be provided as supporting analyses to the Primary Cohort results. The threshold for meeting the primary objective in the Directional Stimulation Cohort will be the same threshold as calculated for the Primary Cohort. In addition, sensitivity analyses will be conducted using the CC and the AT Analysis Set.

An analogy of Prescott’s test⁷ will be computed to test for a period or carryover effect and p-values >0.1 will be deemed as supporting the assumption of no period or carryover effect in the proportion of subjects exceeding threshold for the primary outcome using data from both periods. If the assumption of no period or carryover effect is accepted, target site (STN/GPi), lead type, and center pooling assessments will be made using data from all subjects treated with aDBS in the aDBS Evaluation Phase. If a carryover effect exists, only data from the first period will be used for the analysis.

⁵ Mandan, Arpita (2018). *Two Applications of Summary Statistics: Integrating Information Across Genes and Confidence Intervals With Missing Data*. Master's thesis, Duke University. Retrieved from <https://hdl.handle.net/10161/17533>

⁶ Ekhout, I., van de Wiel, M.A., and Heymans, M.W. (2017), Methods for significance testing of categorical covariates in logistic regression models after multiple imputation: power and applicability analysis. *BMC Med. Res. Methodol.* 17: 129. doi: 10.1186/s12874-017-0404-7

⁷ Nagelkerke, N.J.D., Hart, A.A.M. and Oosting, J. (1986), The Two Period Binary Response Cross - Over Trial. *Biom. J.*, 28: 863-869. doi:10.1002/bimj.4710280715

- [REDACTED]
- [REDACTED]
- [REDACTED]
- [REDACTED]

To test for a treatment difference by target site (STN/GPi), lead type, and center within each mode, Fisher's exact test and Freeman and Halton's extension of Fisher's exact test, respectively, will be computed testing for differences between target sites, lead type, or centers in the proportion of subjects exceeding threshold for the primary outcome using data from both periods. [REDACTED]

- [REDACTED]
- [REDACTED]
- [REDACTED]
- [REDACTED]

P-values >0.1 will be deemed as supporting the assumption of no target site effect, lead type effect, or center effect, respectively, and the data will be considered poolable across the respective variable. If the p-value approaches statistical significance (defined as ≤ 0.1),¹ the proportion exceeding threshold and the lower bound of the 97.5% confidence interval will also be estimated at each target site, lead type, or center, as applicable (eg, if the target sites (STN/GPi) do not allow for pooling the analysis will be conducted by target site for that mode.)

If center(s) causing the significance are identified, variables relating to patient characteristics and other factors will be analyzed to try to identify why this center is showing a different treatment effect.

As part of the additional objectives, "On" time without troublesome dyskinesia will be summarized as absolute change from cDBS Baseline Phase to the Evaluation Phase.

7.9.2 Secondary Objective

7.9.2.1 Secondary Objective

To demonstrate decreased stimulation energy use during the aDBS Evaluation Phase as compared with cDBS.

7.9.2.2 Hypothesis

Two secondary hypotheses are being tested using independent gatekeeper procedures to control the alpha-level as described in section 7.9.1.1. The two secondary alternative hypotheses comparing aDBS (Evaluation Phase) to cDBS (Baseline Phase) separately, are:

- H_{12} : Mean Difference between aDBS dual threshold (Evaluation Phase) minus cDBS (Baseline Phase) for TEED < 0
- H_{22} : Mean Difference between aDBS single threshold (Evaluation Phase) minus cDBS (Baseline Phase) for TEED < 0

7.9.2.3 Endpoint definition

The secondary endpoint is to decrease energy use as measured by TEED during the aDBS Evaluation Phase as compared with TEED during the cDBS Baseline Phase.

TEED is defined as the total energy delivered by an electrical system through the DBS leads over an arbitrary period of time. TEED is determined by the stimulation parameters (e.g., pulse width, frequency, amplitude) and the measured impedance.

The calculation of TEED when using constant voltage is:

$$\text{TEED} = (\text{Voltage}^2 * \text{Frequency} * \text{Pulse width}) / \text{Impedance}$$

The calculation of TEED when using constant current is:

$$\text{TEED} = \text{Current}^2 * \text{Frequency} * \text{Pulse width} * \text{Impedance}$$

The Total TEED will be calculated as a sum of the energy use in the left and right leads. There will be one value per patient for each mode evaluated (eg, cDBS, aDBS Dual Threshold, aDBS Single Threshold).

The reduction in TEED will be calculated as:

$$\text{TEED } \Delta_{\text{aDBS dual threshold mode}} = \text{TEED}_{\text{aDBS dual threshold mode}} - \text{TEED}_{\text{cDBS}}$$

and

$$\text{TEED } \Delta_{\text{aDBS single threshold mode}} = \text{TEED}_{\text{aDBS single threshold mode}} - \text{TEED}_{\text{cDBS}}$$

7.9.2.3.1 TEED calculations by lead type

Calculation with legacy lead models 3387 or 3389

The formulas in Section 7.9.2.3 can be used without modification.

Calculation with SenSight™ system

When SenSight is programmed in Directional Stim Mode or Ring Mode Stimulation, each contact is considered independent.

For each segment that is activated, TEED will be calculated individually using the formulas in Section 7.9.2.3, and then summed to obtain the total TEED for the lead.

7.9.2.3.2 TEED calculation by visit

Computing TEED in cDBS

To compute TEED using the formula above in the cDBS mode, the current drain, pulse-width, frequency, and impedance will be determined from the JSON session data at the cDBS Baseline visit.

Computing TEED in aDBS

To compute TEED using the formula above in an aDBS mode, the average current drain from the JSON session data will be computed using the average stimulation currents from the timeline feature. This will be computed as the average of the currents from the timeline feature using the epochs that align with the analysis set (e.g., As-Treated analysis set uses the actual aDBS mode as reported from the device). Included days should be in the 14 days prior to the visit (ie, Visit 1 or Visit 2). The pulse-width, frequency, and impedance will be determined from the JSON session data at the respective aDBS Evaluation visit (ie, Visit 1 or Visit 2).

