Study Procedures and Assessments	
Subjects will be considered enrolled at the time they sign the informed consent form.
 
Scheduled visits will include the following: Enrollment, LFP Screening, cDBS Baseline, aDBS Setup, Randomization, aDBS Evaluation Visit 1, aDBS Evaluation Visit 2, Long-term follow-up Visit 3, Long-term follow-up Visit 4, Long-term follow-up Visit 5, and Long-term follow-up Visit 6.
 
Subjects participating in the extended access phase prior to commercial approval of aDBS, will have visits every 6 months.
 
The following assessments / data will be collected during the study:
 
 • Concomitant medications • PDQ-39 • EQ-5D-5L • MDS-UPRDS Parts I-IV • Parkinson's Disease Home Diary • VHI • PDSS-2 • aDBS Global Impression of Change score • Patient preference questionnaire • Patient satisfaction questionnaire • Wearable data • Programming session data, including BrainSense data • Event markers (optional) • Adverse Events and Device Deficiencies
Statistics	
Primary and secondary objectives will be analyzed using the FAS. The FAS includes all Primary Cohort subjects, using the intention-to-treat (ITT) principle, who initiate the aDBS Evaluation Phase using the randomized treatment assignment for each subject that was randomized and the programmable treatment assignment for those subjects that may only be configured to one aDBS mode (dual or

Medtronic Business Restricted

single threshold). Safety analyses will be evaluated using the As-Treated (AT) Analysis Set. AT includes all Primary Cohort subjects who are treated with continuous Deep Brain Stimulation (cDBS) and/or adaptive Deep Brain Stimulation (aDBS) during the cDBS Baseline Evaluation Phase and/or the aDBS Evaluation Phase, and Long-term Follow-up Phase and uses the observed treatment used for each subject in each phase.

The Parkinson's Disease Home Diary from the two weeks prior to the Baseline visit (cDBS) and the aDBS Evaluation visits (aDBS) will be used to evaluate the primary objective. The observed proportion will be computed for each aDBS mode separately and compared to the performance goal using a binomial exact test.

The secondary objective will evaluate the decrease in Total Electrical Energy Delivered (TEED) for each aDBS mode compared to cDBS using data from the 14-days prior to the Baseline visit (cDBS) or the respective aDBS Evaluation Visit (aDBS).

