6.1.1. Medtronic Commercially Available DBS System Components

Model B35200 Percept PC INS

The model B35200 Percept PC Neurostimulator with BrainSense™ (Product Firmware Version 7.5, Device Firmware Version 7.5, Core Firmware Version 7.5) is commercially available for DBS Therapy and is part of an active implantable device system for deep brain stimulation and sensing. The DBS system delivers electrical stimulation to targeted regions of the brain, defined by anatomy and/or physiology, to suppress the symptoms associated with a neurologic disorder treatable by brain stimulation. The neurostimulator is a multiprogrammable device that delivers stimulation through 1 or 2 leads. The stimulation settings are stored in programs. Programmable parameters include amplitude, pulse width, rate, and cycling. Percept PC is able to deliver cDBS and also has the capability to sense and record bioelectric data through the DBS leads implanted in the brain.

Percept PC has embedded firmware which adjusts the stimulation output of the device to conform to clinician programmed parameters. The firmware stores data pertinent to device operation and sends the data via radio frequency (RF) telemetry when requested by one of the programmers (clinician programmer or patient programmer). The firmware limits stimulation outputs to within clinician-defined ranges and modes.

The commercially available Model B35200 Percept PC INS will be implanted prior to subject enrollment in the study. The commercially available Model B35200 Percept PC INS contains the aDBS FW, but the FW is not active.

DBS Leads (Includes models 3387, 3389, B33005 and B33015)

The Models 3387 and 3389 DBS Leads are composed of a polyurethane protective sheath with four platinum/iridium electrodes located at the distal end, which are used to deliver the electrical stimulation to the target site.

The Model 3387 DBS Lead features wide (1.5 mm) spacing between each of the four electrodes at the distal end. The Model 3389 DBS Lead features narrow (0.5 mm) spacing between each of the four electrodes at the distal end.

The Models B33005 and B33015 SenSight Leads are composed of a polyurethane protective sheath with eight platinum/iridium electrodes located at the distal end (in a 1-3-3-1 configuration with the second and the third electrodes separated into three separate electrodes spaced 120° from the center of each segment), which are used to deliver the electrical stimulation to the target site.

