13.2.2. Factors That May Compromise the Outcome or Interpretation of the Results

Missing PD Home Diary Data

PD Home Diary non-compliance or incorrect completion are most concerning in the assessment of the primary effectiveness objective. PD Home Diaries will be collected, regardless of completeness or accuracy of completion. PD Home Diaries and other efficacy data collected while the subject is in the wrong treatment assignment or stimulation is inactive will be included in analyses, following [Section 13.4.5](#).

PD Home Diary compliance will be continuously monitored throughout the duration of the study to ensure that compliance is maintained.

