13.5.3. Endpoint definition

The secondary endpoint is to decrease energy use as measured by TEED during the aDBS Evaluation Phase as compared with TEED during the cDBS Baseline Phase. The Total TEED will be calculated as a sum of the energy use in the left and right leads. There will be one value per patient for each mode evaluated (eg, cDBS, aDBS Dual Threshold, aDBS Single Threshold).

The reduction in TEED will be calculated as:

$$\text{TEED } \Delta_{\text{aDBS dual threshold mode}} = \text{TEED}_{\text{aDBS dual threshold mode}} - \text{TEED}_{\text{cDBS}}$$

and

$$\text{TEED } \Delta_{\text{aDBS single threshold mode}} = \text{TEED}_{\text{aDBS single threshold mode}} - \text{TEED}_{\text{cDBS}}$$

Computing TEED in cDBS

To compute TEED using the formula in [Section 9.15.2](#) in the cDBS mode, the current drain, pulse-width, frequency, and impedance will be determined from the JSON session data at the cDBS Baseline visit.

Computing TEED in aDBS

To compute TEED using the formula in [Section 9.15.2](#) in an aDBS mode, the average current drain from the JSON session data will be computed using the average stimulation currents from the timeline feature. This will be computed as the average of the currents from the timeline feature using the epochs

Medtronic Business Restricted

that align with the analysis set (e.g., As-Treated analysis set uses the actual aDBS mode as reported from the device). Included days should be in the 14 days prior to the visit. The pulse-width, frequency, and impedance will be determined from the JSON session data at the aDBS Evaluation visit.

Impedance

Leads programmed with monopolar settings will use the electrode unipolar impedance between the case and the active electrode. If 2 cathodes are used (dual monopolar settings), TEED will be calculated for each contact separately, and total TEED will be determined for the lead as the sum of the two TEED. Leads programmed to bipolar will use the impedance between the active electrodes. In case electrode impedance was not collected at cDBS Baseline or aDBS Evaluation Phase, impedance from aDBS Setup would be used.

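### The protocol synopsis and the detailed TEED sections define the cDBS comparator differently, and the detailed rule compares a single-visit cDBS value with a 14-day aDBS average

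*SAP*

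**What the plan says.** The secondary endpoint compares TEED in each aDBS mode with TEED in the cDBS Baseline Phase. The alternative is a mean difference below zero (Protocol 13.5.2, SAP 7.9.2.2).

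The Statistics entry of the Protocol synopsis describes this comparison as "using data from the 14-days prior to the Baseline visit (cDBS) or the respective aDBS Evaluation Visit (aDBS". That is the same window on both sides.

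The detailed sections differ. For cDBS, SAP 7.9.2.3.2 says that "the current drain, pulse-width, frequency, and impedance will be determined from the JSON session data at the cDBS Baseline visit", and Protocol 13.5.3 has the same rule ("and impedance will be determined from the JSON session data at the cDBS Baseline visit"). For aDBS, pulse width, frequency and impedance also come from the visit, but the current does not: "This will be computed as the average of the currents from the timeline feature using the epochs that align with the analysis set". The window is then limited: "Included days should be in the 14 days prior to the visit (ie, Visit 1 or Visit 2". Neither detailed section says how epochs with stimulation off are to be treated.

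**The concern.** Two things are wrong on the face of the text. First, an analyst cannot follow both the synopsis and the detailed sections when deriving the cDBS value. This is the only secondary endpoint. It is formally tested within each mode, behind the primary hypothesis as gatekeeper.

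Second, under the detailed rule the comparator is a value read at one visit and the test condition is an average of current over time. SAP 7.9.2.3 defines TEED as energy delivered over a period. A single-visit value cannot reflect time with stimulation off, or the off part of a cycling program, and Protocol 6.1.1 lists cycling as a programmable option ("Programmable parameters include amplitude, pulse width, rate, and cycling"). A timeline average may reflect both. Off-time that is identical in the two phases could then appear as an aDBS saving, in the direction of the alternative.

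**Working it through.** **Step 1. The texts side by side.**

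| Source | cDBS current | aDBS current |
|---|---|---|
| Protocol synopsis, Statistics | 14 days before the Baseline visit | 14 days before the Evaluation visit |
| Protocol 13.5.3 | session data at the Baseline visit | timeline average, days within the 14 before the visit |
| SAP 7.9.2.3.2 | session data at the Baseline visit | timeline average, days within the 14 before the visit |

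The SAP agrees with the body of the Protocol. The conflict is between the synopsis and both detailed sections.

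**Step 2. The plan's own sample size.** The inputs from SAP 7.9.2.4 are one-sided alpha 0.0125, difference 22, SD 35 and N = 36. The effect size is 22/35 = 0.629. The noncentrality is 0.629 × √36 = 3.77, and the t-test power is 0.918. The smallest N for 90% power is 34. The stated 36 subjects with at least 90% power is reproduced. (The next SAP sentence attaches 0.629 to an SD of 36, but 22/36 = 0.611, with power 0.902.) The choice of cDBS rule does not alter this if the SD holds.

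**Step 3. Size of the artefact for one subject.** Assume the same on-current in both phases, the same off-time fraction f in both, and zero current for off epochs in the aDBS average. The true change is 0. Relative to the Baseline-visit value:
- false fall in energy from off-time alone = f
- false fall through the plan's formula, which squares the mean current = 1 − (1 − f)²

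| Off-time per day | f | Off-time alone | With mean current squared |
|---|---|---|---|
| 1 h | 1/24 | 4% | 1 − (23/24)² = 8% |
| 2 h | 2/24 | 8% | 1 − (22/24)² = 16% |
| 4 h | 4/24 | 17% | 1 − (20/24)² = 31% |
| 8 h | 8/24 | 33% | 1 − (16/24)² = 56% |

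The gap between the last two columns comes from squaring a mean, which is a separate matter from the mismatch in source.

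**Step 4. Effect on the test.** The mean cDBS TEED is not in the documents, so take 44, 70 and 100 units as an assumed range. The first two follow if the expected falls of 22 and 35 (SAP 7.9.2.4) are each about half of the cDBS level, half being the average power saving cited in Protocol 3.1. Apply the same off-time to every subject, keep N = 36 and SD 35, and set the true effect to 0. The bias in units is the cDBS level times the false fall, and the nominal rejection rate is 0.0125.
- Off-time alone: 5% of 100 is 5 units, rejection 0.079. 10% of 70 is 7 units, rejection 0.139. 10% of 100 is 10 units, rejection 0.278.
- With the mean squared, 5% off (fall 1 − 0.95² = 9.75%): 4.3, 6.8 or 9.8 units at 44, 70 or 100, rejection 0.063, 0.133 or 0.265.
- With the mean squared, 10% off (fall 1 − 0.90² = 19%): 8.4, 13.3 or 19.0 units, rejection 0.195, 0.483 or 0.815.

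If both sides used the same 14-day rule, the shared off-time would cancel and the rate would return to 0.0125.

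**The case against.** The best defence is that cDBS is constant by design. Protocol 3.1 describes its settings as not varying over time. Inclusion criterion 4 requires stable parameters, and Protocol 9.7.1 allows only clinically necessary changes. For constant output the visit value equals the 14-day mean, while aDBS varies and has to be averaged. SAP 7.9.2.3.2 also does not say that off epochs count as zero, and no document says what the timeline records when stimulation is off. An As-Treated sensitivity analysis is planned, using the mode the device reports, and SAP 7.9.3.11 lists aDBS on time among the device summaries.

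Much of this stands, and it makes the artefact possible rather than shown. It does not remove the conflict. The stability rules restrain investigators' changes but do not address off-time or cycling. The As-Treated and Complete-Case analyses leave the cDBS value as the visit reading.

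A reader might infer more than the documents support:
- **Paused aDBS lowers the average.** Protocol 9.9.1 says pausing delivers the suspend amplitude, which is not zero current.
- **cDBS setting changes before Baseline favour aDBS.** They can go either way. An amplitude reduction shortly before the visit would make the snapshot understate cDBS energy.
- **Inactive time is certain to enter the aDBS average.** Protocol 13.2.2 does say that efficacy data collected while "stimulation is inactive will be included in analyses", but under a heading on missing diary data and with a pointer to the diary rules in 13.4.5. It is not a TEED rule.
- **Cycling is in use.** The Protocol lists it only as a device capability.

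**Conclusion.** The point holds as a conflict between texts and a mismatch in measurement. The synopsis and the two detailed sections give different cDBS windows, and the detailed rule measures the two sides of a tested comparison in different ways. No planned sensitivity analysis changes the cDBS side.

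A bias toward a TEED decrease follows only on two conditions: off-time or cycling is common to both phases, and off epochs enter the aDBS average. Its size then depends on off-time and on the mean cDBS TEED, neither of which the documents give, so the percentages and rejection rates above are illustrations and not predictions. The documents do not support the stronger conclusion that the energy claim will be met without any adaptive effect.

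This should be fixed. It concerns a gated secondary endpoint, and the primary endpoint and the planned 36 subjects are unaffected.

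**What to change.** Reconcile the synopsis, Protocol 13.5.3 and SAP 7.9.2.3.2 so that cDBS and aDBS current come from the same source, the device timeline, over the 14 days before the respective visit. State one rule for off epochs and apply it to both sides. The files should already exist: Passive Sensing runs through the cDBS Baseline Period (Protocol 9.8.2), and the session with BrainSense data is uploaded at the Baseline visit (9.8.3).

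The documents do not confirm that the timeline records delivered current during cDBS on both leads. Eligibility needs an adequate signal on only one lead, while TEED sums both. A fallback is therefore part of the fix. Where the cDBS timeline lacks delivered current for a lead, use the Baseline-visit current, compute that subject's aDBS TEED over stimulation-on epochs only, and flag the subject. Add a sensitivity analysis that uses stimulation-on epochs for all subjects.

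The cost is a wording change and one extra derivation. An unknown number of subjects would be on the fallback, and the stated saving may be smaller.
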